- f Vital signs include 10-minute seated arterial blood pressure, pulse rate, and body temperature. Height will be measured at Day 1 only. Weight will be measured at Weeks 0, 24, 52, 76, and 104. Body weight will be measured with a balance beam scale, if possible.
- g Questionnaires should be completed before any other procedures are performed. Questionnaires should be performed in the following order: Patient's Global Assessment, SHAQ, Mahler BDI (at Day 1) followed by Mahler TDI at the subsequent visits, SGRQ, Leicester Cough Index, and EQ-5D. The Mahler BDI/TDI administrator must be blinded to other assessments. The Physician's Global Assessment (VAS) may be performed after other assessments at the visit are completed.
- h For all subjects, samples will be collected predose and immediately after the end of IMP infusion at Weeks 0 (Day 1), 4, 8, and 16.
- i For subjects who have provided informed consent for the rich PK sampling, additional samples will be collected on Days 3, 5, 15, and 22 (in addition to the pre- and postdose samples at Weeks 0, 4, 8, and 16; see footnote h).
- j See Section 7.4.3 for list of routine laboratory assessments. Urine protein:creatinine ratio to be performed if dipstick urinalysis reveals at least 3+ protein. Microscopic urinalysis to be performed if blood is present.
- k The DLCO measurements will be corrected for hemoglobin level, and spirometry assessments will be centrally adjudicated.
- l Digital ulcers are those distal to the metacarpal phalangeal joints. New or worsening digital ulcers, or at any other site on the body, will be captured as AEs.

CCI

CCI

- o Adverse events should also be assessed for occurrence during the periods between trial visits.

Table 2 Schedule of Assessments – Week 56 through Safety Follow-up

Trial Period	Weeks During Double-blind Treatment Period (Visit Window ±5 days)													ET ^a	Safety Follow-up Number weeks post last visit (±5 days)		Survival Follow-up Post Last Trial Visit
	56	60	64	68	72	76	80	84	88	92	96	100	104		4	12	
Week	393	421	449	477	505	533	561	589	617	645	673	701	729				
Trial Day	393	421	449	477	505	533	561	589	617	645	673	701	729				
HRCT													X	X			
12-lead ECG (locally read)						X							X	X		X	
Urine pregnancy test ^{b,c}	X	X	X	X	X	X	X	X	X	X	X	X	X	X	X	X	
Physical examination	X ^d	X ^d	X ^d	X ^d	X ^d	X	X ^d	X ^d	X ^d	X ^d	X ^d	X ^d	X	X	X ^d	X	
Vital signs, weight ^e	X	X	X	X	X	X	X	X	X	X	X	X	X	X	X	X	
Mahler TDI and SGRQ ^f			X			X			X				X	X		X	

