Patient's Global Assessment, Leicester Cough Index, SHAQ, EQ-5D, and Physician's Global Assessment ^f						X							X	X			
IMP administration	X	X	X	X	X	X	X	X	X	X	X	X					
Routine hematology, clinical chemistry, urinalysis ^g		X	X	X		X		X	X	X		X	X	X	X	X	
Pulmonary function tests (FVC, DLCO) ^h			X			X			X				X	X		X	
mRSS			X			X			X				X	X		X	
Digital ulcer counts ⁱ			X			X			X				X	X		X	
Serum for ADA						X							X	X	X	X	
CCI																	
Concomitant medications/procedures	X	X	X	X	X	X	X	X	X	X	X	X	X	X	X	X	

Trial Period	Weeks During Double-blind Treatment Period (Visit Window ± 5 days)													ET ^a	Safety Follow-up Number weeks post last visit (± 5 days)		Survival Follow-up Post Last Trial Visit
	56	60	64	68	72	76	80	84	88	92	96	100	104		4	12	Every 12 Weeks
Week																	
Trial Day	393	421	449	477	505	533	561	589	617	645	673	701	729				
Adverse events ^j	X	X	X	X	X	X	X	X	X	X	X	X	X	X	X	X	
Vital status ^k																	X

ADA = antidrug antibodies; AE = adverse event; BDI = Baseline Dyspnea Index; DLCO = diffusion capacity of the lung for carbon monoxide; ECG = electrocardiogram; ET = early termination; FVC = forced vital capacity; HRCT = high resolution computed tomography; IMP = investigational medicinal product; mRSS = modified Rodnan skin score; SGRQ = St. George Respiratory Questionnaire; SHAQ = Scleroderma Health Assessment Questionnaire; TDI = Transition Dyspnea Index; VAS = visual analog scale.

- a Subjects who discontinue IMP for any reason should complete the ET visit as soon as possible, but within 2 weeks of IMP discontinuation, and then the remaining scheduled trial visits. At a minimum, the subject is expected to complete the trial visits at Weeks 12, 24, 36, 52, 64, 76, 88, and 104, as well as the Safety Follow-up period Week 12 visit. Subjects with discontinued IMP can come to the other scheduled visits during the trial period according to the Investigator's judgment. Subjects who withdraw from the treatment period would have an early termination visit followed by entrance into the Safety Follow-up Period. Subjects who withdraw from the trial (eg, withdraw consent, lost to follow up, or death; see Section 5.5.2) would not have any additional trial visits. All subjects will be followed up by the site approximately every 12 weeks for survival from the subject's last trial visit until death or the end of the trial.

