3.3 Risk-Benefit Analysis

Available data from preclinical studies with cynomolgus monkeys showed a favorable toxicological safety profile for abituzumab. No potential safety issues emerged from these studies other than antidrug antibody (ADA) formation.

CCI [Redacted]

[Redacted]

[Redacted]

[Redacted]

[Redacted]

[Redacted]

[Redacted]

[Redacted]

[Redacted]

[Redacted]

[Redacted]

[Redacted]

[Redacted]

CCI

CCI [REDACTED] the digital ulcer count will be also be assessed at scheduled visits (see [Table 1](#) and [Table 2](#)). Only an increase in number or worsening of digital ulcers would be considered a safety issue since SSc itself can be associated with digital ulcer formation. Together, these data sets will provide monitoring for impaired wound healing or skin breakdown. All blistering or Grade ≥ 3 AEs in the skin and subcutaneous tissue disorders system organ class (SOC), will be designated as AEs of special interest (AESI). Any cutaneous reaction of Grade 1 or 2 that is not responding to specific treatment or is worsening will also be designated as an AESI. The occurrence of AESI or cutaneous serious AEs (SAEs) will be reviewed by an independent panel of dermatologists to provide guidance for further investigation and interpretation of these events, and advise the IDMC whether any actions to modify clinical trial conduct should be considered. An IDMC will review safety data to ensure safety of all subjects enrolled in the trial. If subjects have significant worsening of lung function, they may start rescue medication, as appropriate. No additional risk minimization measures are considered necessary at this time for studying the effects of abituzumab in subjects with SSc-ILD.

Based on the available nonclinical and clinical data to date, the conduct of the trial specified in this protocol is considered justifiable.

4 Trial Objectives

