6.5.5 Management of Specific Adverse Events or Adverse Drug Reactions

Subjects with cutaneous AESI thought to be related to IMP and Grade ≥ 3 in severity should have the IMP withheld. If subsequently the event has sufficiently resolved, re-initiation of IMP at half of the original dose may be considered by the Investigator after discussion with the CRO Medical Monitor.

Clinically Meaningful Disease Progression

Subjects meeting one or both of the below criteria will be considered as having clinically meaningful disease progression:

1. **SSc-ILD:** one of the following (in the absence of causative intercurrent illness) on at least 2 occasions within approximately 4 weeks (per OMERACT criteria):
 - Relative decrease from baseline in FVC % predicted $\geq 10\%$;
 - Relative decrease from baseline in FVC % predicted of $\geq 5\%$ to $< 10\%$ and relative decrease from baseline in DLCO % predicted $\geq 15\%$.
2. **SSc progression other than ILD:** new onset of one or more of the following:
 - Scleroderma renal crisis;
 - Left ventricular failure (defined as ejection fraction $\leq 45\%$);
 - Pulmonary arterial hypertension requiring treatment.

Subjects with clinically meaningful disease progression of SSc-ILD should be considered for change in therapy according to the guidance below:

- Subjects taking submaximal doses of mycophenolate (MMF < 3 g/day or MPS < 2160 mg/day) should have an increase to 3 g/day or 2160 mg/day, respectively, as tolerated. The IMP should be continued (unless meeting criteria for withdrawal from IMP, refer to Section 5.5.1).
- Subjects taking maximal doses of mycophenolate should have the IMP discontinued and be treated according to the local standard of care. If a nonbiologic immunosuppressant (such as cyclophosphamide [intravenous or oral]) is initiated, then mycophenolate must be discontinued. Subjects withdrawn from IMP should complete the early termination visit.

After the change in therapy as described above for progression of SSc-ILD, subjects would fulfill criteria for further disease progression if meeting 1 of the 2 specified criteria based on change in FVC and DLCO (ie, using the clinical data from the time of change in therapy as the new 'baseline'). Such subjects should be switched from mycophenolate to other local standard of care with discontinuation of IMP.

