7.5 Pharmacokinetics

Serum samples for the determination of abituzumab concentrations will be collected from all subjects at the time points given in Table 1. In a subset of subjects who give separate consent to provide additional PK samples (rich PK sampling), additional samples will be collected at the time points given in Table 1 (see footnote i).

For the PK evaluation, serum levels of abituzumab will be analyzed by the bioanalytical laboratory using an appropriate validated method.

The actual date and time of sample collection will be recorded.

Instructions for the collection, storage, handling, and shipping of PK samples will provided in the PPD Flow Chart.

CCI [REDACTED]

[REDACTED]

[REDACTED]

[REDACTED]

[REDACTED]

CCI

8 Statistics

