8.1 Sample Size

Based on reference data from randomized clinical trials in SSc-ILD and IPF, an expected improvement of 150 mL in the annual rate of absolute FVC change (mL) is assumed for abituzumab 1500 mg versus placebo with a common standard deviation of 300 mL. CCI

The inclusion of abituzumab 500 mg in conjunction with abituzumab 1500 mg will support abituzumab exposure-response analysis for dosing optimization.

A blinded sample size review is planned after at least 50% of the subjects complete their first year on treatment. The review will either lead to an increase in the total sample size or to a continuation of the trial with the original sample size. Following [Kieser 2003](#), the estimated one-sample variance will be adjusted for bias. If the adjusted standard deviation is more than 10% larger than the hypothesized standard deviation (ie, 330 mL or more), then the sample size may be increased by up to 40 subjects. Details will be provided in the Statistical Analysis Plan.

Hypothesis Testing

The primary endpoint is the annual rate of absolute FVC change in volume (mL).

- The null hypothesis is:

H0: There is no improvement in annual rate of absolute FVC change for the abituzumab 1500 mg arm compared with the placebo arm on top of stable mycophenolate.

- The alternative hypothesis is:

H1: There is an improvement in annual rate of absolute FVC change for the abituzumab 1500 mg arm compared with the placebo arm on top of stable mycophenolate.

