
Quality of life endpoints will be summarized according to their scoring instructions. Continuous variable will be analyzed using ANCOVA unless otherwise specified. Categorical variable will be analyzed using categorical methods. Details will be specified in the Statistical Analysis Plan.

Pharmacokinetic Analyses

A Population PK model will be developed. The influence of covariates on PK parameters will be assessed. From the final Population PK model, individual estimates of the PK parameters and exposure parameters (AUC, C_{max} , and C_{min}) will be derived. The exposure parameters may be used for further exposure-response assessment.

CCI [REDACTED]

[REDACTED]

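### After Day 1 no scheduled ADA sample has a paired abituzumab concentration, so a change in clearance after Week 16 cannot be detected

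*Protocol*

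**What the plan says.** **Concentrations.** Footnote h to Table 1 of the protocol reads "For all subjects, samples will be collected predose and immediately after the end of IMP infusion at Weeks 0 (Day 1), 4, 8, and 16". For subjects who consent to rich PK sampling, footnote i says "additional samples will be collected on Days 3, 5, 15, and 22". Section 7.5 places the general PK time points in Table 1 alone: "Serum samples for the determination of abituzumab concentrations will be collected from all subjects at the time points given in Table 1". Table 2, which runs from Week 56 through follow-up, has no PK row.

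**ADA.** The ADA row is marked on Day 1 and at Weeks 24 and 52 in Table 1. In Table 2 it is marked at Weeks 76 and 104, early termination (ET), and Safety Follow-up Weeks 4 and 12. No footnote to that row says whether the draw is before or after the infusion.

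**Purpose.** Section 5.2.2 gives an exposure-response relationship as the reason for two doses, and Section 8.1 says that including 500 mg "will support abituzumab exposure-response analysis for dosing optimization". Section 4.2 lists immunogenicity and PK among the secondary objectives. Section 8.5.3 plans a population PK model with covariate assessment, and adds: "The exposure parameters may be used for further exposure-response assessment".

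**The concern.** For a monoclonal antibody, ADA is an obvious reason for clearance to change during treatment. Section 3.3 says of the monkey studies: "No potential safety issues emerged from these studies other than antidrug antibody (ADA) formation". The plan collects both kinds of sample, but never together once treatment has begun.

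Two things are at stake:

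- **Exposure-response.** If a subject's clearance rises after Week 16, the model will keep assigning the exposure implied by the early kinetics. The exposure axis is then wrong for that subject over most of the period in which FVC is measured.
- **Reading ADA results.** Circulating drug can interfere with an ADA assay. A negative result during treatment is easier to trust when the drug level at that visit is known, and here it is not.

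**Working it through.** The plan states no figure on this point, so the check is a reconstruction of the schedule.

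**Inputs.** PK weeks are 0, 4, 8 and 16 (Table 1, footnote h). ADA weeks are 0, 24, 52, 76 and 104, plus ET and Safety Follow-up Weeks 4 and 12 (Tables 1 and 2). Infusions are every 4 weeks from Week 0 to Week 100 (Section 6.2). Post-baseline FVC is at Weeks 12, 24, 36, 52, 64, 76, 88 and 104. Trial day = 7 × week + 1, which matches the printed days (Week 16 = Day 113; Week 24 = Day 169).

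**1. Pairing.** {0, 4, 8, 16} and {0, 24, 52, 76, 104} share only Week 0. Scheduled pairs after baseline are therefore 0 of 4 during treatment, and 0 of 6 with the two follow-up visits. ET also has ADA without PK.

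**2. Gap.** Last PK to first scheduled post-baseline ADA is 169 − 113 = 56 days, or 50 to 62 days with ±3-day windows at both visits.

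**3. Share of treatment after the last PK sample.**

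| Quantity | To Week 52 | To Week 104 |
|---|---|---|
| Weeks | (52 − 16)/52 = 36/52 = 69% | (104 − 16)/104 = 88/104 = 85% |
| Infusions | 8 of the 13 before Week 52 = 62% | 21/26 = 81% |
| Post-baseline FVC visits | 3 of 4 | 7 of 8 |

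**4. What the model can and cannot do.** Average exposure is proportional to dose ÷ clearance. The dose is known at every infusion, because Section 6.9 has the exact volume recorded. Clearance is informed only by samples up to Week 16, so later exposure is a projection that assumes clearance stays the same.

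**5. Illustration of a missed change.** The assumptions, none of them from the documents, are linear, dose-proportional kinetics and a clearance rise of 1.5-, 2- or 3-fold after Week 16. A 1500 mg subject then has the average exposure of 1500/1.5 = 1000 mg, 1500/2 = 750 mg or 1500/3 = 500 mg, while the model still assigns 1500 mg. No ADA incidence is given, so the effect on the whole exposure-response analysis cannot be computed.

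**6. With the fix.** One concentration at each ADA visit raises pairing from 0/4 to 4/4 during treatment and from 0/6 to 6/6 with follow-up. The last on-treatment measurement moves from Week 16 to Week 104.

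**The case against.** The strongest reply is that this is a sampling preference for an analysis worded as optional, with a size that depends on facts the reader cannot see. Much of that stands.

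- Section 8.5.3 says only that exposure parameters may be used. Sections 5.2.2 and 8.1 are firmer, so the point keeps its relevance.
- The ADA endpoint in Section 8.3.3 is the incidence of positive titers to Week 116. The schedule delivers that, and no stated objective is to relate ADA to exposure.
- Predose samples at Weeks 4, 8 and 16 could show a clearance rise that begins early. Whether five infusions characterise steady state depends on the half-life, which is not visible. The 85% is calendar time, not lost information.
- The ADA statement in Section 3.3 concerns monkeys given a humanized antibody. Much of what follows it is redacted, so it says little about risk in patients.

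Four stronger readings are tempting, and the documents do not support them:

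- **Exposure after a reduced-dose restart is lost.** Section 6.5.5 allows such a restart, but the volume of each infusion is recorded, so the model can handle a reduced dose without a new sample.
- **ADA negatives can never be checked for interference.** Safety Follow-up Weeks 4 and 12 are timed from Week 104 and the last dose is at Week 100. For completers these draws come about 8 and 16 weeks after dosing, when less drug should remain. The difficulty is confined mainly to on-treatment draws.
- **ADA is sampled only from Week 24.** There is a Day 1 draw. A subject who stops treatment "should complete the ET visit as soon as possible, but within 2 weeks of IMP discontinuation", so an ET draw can come before Week 24. A concentration there would be incidental: ET falling on a PK visit, or an optional unscheduled sample under Section 7.1.2.
- **The primary result is at risk.** The test compares randomized 1500 mg with placebo and uses no concentrations.

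**Conclusion.** The point holds as a cheap improvement to the protocol. After Day 1, no scheduled ADA sample has a scheduled concentration beside it, and 21 of 26 infusions and 88 of 104 weeks follow the last PK sample. The planned model can project exposure over that time, but scheduled samples cannot show whether clearance changed, for example because of ADA. On-treatment ADA negatives cannot be read against a drug level.

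The schedule counts are certain on the visible text: footnote h and Section 7.5 fix the PK times despite nearby redactions. The consequences are not certain. They turn on half-life, assay drug tolerance and ADA incidence, none of which is visible, and the clearance multiples are illustrations only.

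No reported result depends on this. Section 10 of the SAP addendum, written after early termination, plans no PK analyses for the abbreviated report, and its table and listing shells include no ADA output. The point therefore concerns the design and any reuse of it, together with any serum still held.

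**What to change.** In Tables 1 and 2, add a PK sample to the ADA draw at Weeks 24, 52 and 76, and state that both are taken predose at these dosing visits. Add a PK sample to the ADA draw at Week 104, ET, and Safety Follow-up Weeks 4 and 12. Point Section 7.5 to Table 2 as well as Table 1. In Section 8.5.3, name ADA status as a time-varying covariate in the population PK model.

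For this trial, where a schedule change can no longer help, the alternative is to assay abituzumab in banked ADA serum, if any was kept and if consent and sample stability allow.

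**Cost.** No new visit or procedure is needed. Planned active-arm subjects number about 175 × 3/5 = 105. At up to 7 added assays each, the ceiling is 7 × 105 = 735 assays. Most completers would have 6, because ET does not apply to them. Section 6.10 already lets the PK laboratory be unblinded so that placebo samples need not be assayed. The rest is a schedule amendment and extra tubes or aliquots at blood draws already planned.

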3.1 Abituzumab

Abituzumab, also known as EMD 525797 or DI17E6, is a humanized monoclonal immunoglobulin G2 (IgG2) antibody against the human α v-integrin subunit. Integrins are transmembrane proteins that exist as heterodimers of an alpha (α) and a beta (β) subunit. The binding of abituzumab to the α v subunit inhibits the binding of all α v integrins (ie, α v β x) to its extracellular matrix ligands (eg, latency associated protein of transforming growth factor [TGF]- β 1, vitronectin, and fibronectin). This inhibition of α v integrin function is anticipated to lead to a reduction in the activation of TGF- β , a major mediator of fibrosis. Abituzumab thus has potential to have antifibrotic activity.

Abituzumab drug product is currently formulated for administration via intravenous infusion. The target indication of the development program is SSc-ILD. For this trial in subjects with SSc-ILD, abituzumab will be administered at doses of 500 or 1500 mg at 4-week intervals on a background of stable mycophenolate.

Refer to the Investigator's Brochure (IB) for further information about the nonclinical and clinical programs and Guidance for the Investigator.

This clinical trial will be conducted in compliance with the clinical trial protocol, ICH GCP, and any additional applicable regulatory requirements.

3.2 Trial Rationale

This is a Phase II, multicenter, double-blind, placebo-controlled, parallel-group trial investigating the efficacy, safety, tolerability, and immunogenicity of abituzumab at 2 dose levels in subjects with SSc-ILD who are treated with a stable mycophenolate regimen.

An interim futility analysis will be performed by an independent third party statistician when approximately 88 subjects have either completed 52 weeks of treatment or prematurely discontinued from the trial. The results of the interim futility analysis will be reviewed confidentially by the IDMC, who will make a recommendation to the Sponsor on continuing or stopping the trial for futility, based on predefined criteria in the IDMC charter. If the Sponsor follows an IDMC recommendation to stop the trial, then enrollment and treatment with IMP will be stopped and subjects will be required to complete the early termination visit and move into the Safety Follow-up Period.

The trial design takes into consideration an emerging trend in the treatment of SSc-ILD for use of mycophenolate as an alternative to cyclophosphamide, given the recent data regarding similar effects on pulmonary function but more favorable safety profile of the former and thus its potential for long-term use (Tashkin 2016, Volkman 2015). The potential antifibrotic effects of abituzumab could have complementary effects on the disease process to the immunosuppressive effects of mycophenolate. Therefore, this trial will evaluate whether abituzumab is associated with benefit when added to stable mycophenolate treatment.

3.3 Risk-Benefit Analysis

Available data from preclinical studies with cynomolgus monkeys showed a favorable toxicological safety profile for abituzumab. No potential safety issues emerged from these studies other than antidrug antibody (ADA) formation.

CCI [Redacted]

[Redacted]

[Redacted]

[Redacted]

[Redacted]

[Redacted]

[Redacted]

[Redacted]

[Redacted]

[Redacted]

[Redacted]

[Redacted]

[Redacted]

CCI

CCI [REDACTED] the digital ulcer count will be also be assessed at scheduled visits (see [Table 1](#) and [Table 2](#)). Only an increase in number or worsening of digital ulcers would be considered a safety issue since SSc itself can be associated with digital ulcer formation. Together, these data sets will provide monitoring for impaired wound healing or skin breakdown. All blistering or Grade ≥ 3 AEs in the skin and subcutaneous tissue disorders system organ class (SOC), will be designated as AEs of special interest (AESI). Any cutaneous reaction of Grade 1 or 2 that is not responding to specific treatment or is worsening will also be designated as an AESI. The occurrence of AESI or cutaneous serious AEs (SAEs) will be reviewed by an independent panel of dermatologists to provide guidance for further investigation and interpretation of these events, and advise the IDMC whether any actions to modify clinical trial conduct should be considered. An IDMC will review safety data to ensure safety of all subjects enrolled in the trial. If subjects have significant worsening of lung function, they may start rescue medication, as appropriate. No additional risk minimization measures are considered necessary at this time for studying the effects of abituzumab in subjects with SSc-ILD.

Based on the available nonclinical and clinical data to date, the conduct of the trial specified in this protocol is considered justifiable.

4 Trial Objectives

